4.2 Study Procedures

Study population: Patients undergoing elective abdominal surgery

Grouping: Group A: $\text{FiO}_2=30\%$ (if $\text{SpO}_2<94\%$, increase FiO_2 ; if $\text{FiO}_2\geq40\%$, the patient was excluded); Group B: $\text{FiO}_2=40\%$; Group C: $\text{FiO}_2=60\%$; Group D: $\text{FiO}_2=80\%$. Inspired oxygen concentrations were adjusted to the respective group levels after the start of surgery.

Trial protocol: Patients entered the operating room, preoxygenated for 3 minutes, followed by anesthesia induction. After the drugs took full effect, tracheal intubation was performed. Inspired oxygen concentrations were adjusted to the respective group levels after the start of surgery. The first lung recruitment was performed 10 minutes later. The second lung recruitment was performed after lung compliance returned to baseline. All patients underwent lung recruitment immediately at the end of surgery. Respiratory mechanics parameters, hemodynamic parameters, etc., were recorded. The incidence of hypoxemia during PACU stay and postoperative atelectasis evaluated by ultrasound were recorded.

4.3 Indications

Atelectasis after general anesthesia

4.4 Study Endpoints

Incidence of pulmonary complications within 3 days after surgery.

5. Study Subjects

5.1 Study Population

Patients undergoing elective abdominal surgery;

5.2 Inclusion Criteria

Patients with ASA physical status I - II ;

Patients who voluntarily participate in the study and sign the informed consent form;
Patients undergoing elective abdominal surgery under general anesthesia;
Gender unlimited, aged 18-64 years, BMI 18-25 kg/m²;
Expected operation time ≥1.5 hours, and intraoperative blood loss ≤500 ml.

5.3 Exclusion Criteria

Previous thoracic surgery; chest X-ray or CT indicating pneumothorax or pulmonary bullae;
Pulmonary diseases: chronic bronchitis, asthma, moderate to severe obstructive ventilatory dysfunction; preoperative pulse oxygen saturation (SpO₂) <90% in room air or <95% with oxygen inhalation; contraindications to lung recruitment: high intracranial pressure, hypovolemic shock, right heart failure;
Severe heart disease (New York Heart Association, NYHA class III or IV; acute coronary syndrome or persistent ventricular tachyarrhythmia); participation in other interventional studies or refusal to enroll.

5.4 Exclusion Criteria

In Group A (FiO₂=30%), if SpO₂<94%, FiO₂ was increased; if FiO₂≥40%, the patient was excluded.

5.5 Recruitment Process

Subjects were visited one day before surgery to understand whether their medical history met the inclusion and exclusion criteria. After confirmation, the experimental process and anesthesia method were communicated with the family members. If the subjects and their families agreed, the anesthesia consent form and clinical trial informed consent form were signed. Eligible subjects were enrolled and randomly grouped.

5.6 Criteria for Terminating the Study

Considerations for the safety of subjects. For example, situations where it is inappropriate to continue the study, including: worsening of the condition, serious adverse events, poor compliance, etc. Postoperative occurrence of surgery-related complications such as postoperative bleeding requiring reoperation should result in termination of the study.

6. Research Methods and Technical Route

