9.1 Definition and Assessment of Adverse Events

Adverse Event (AE) refers to any untoward medical event that occurs after a subject receives the investigational product, which may present as symptoms, signs, diseases, or abnormal laboratory tests, but is not necessarily causally related to the investigational product.

Serious Adverse Event (SAE) refers to an adverse medical event that occurs after a subject receives the investigational product, including death, life-threatening conditions, permanent or severe disability or functional loss, need for hospitalization or prolongation of hospitalization, and congenital anomalies or birth defects.

Adverse Drug Reaction (ADR) refers to any harmful or unintended reaction that may be related to the investigational product in clinical trials. There is at least a reasonable possibility of a causal relationship between the investigational product and the adverse event, i.e., the correlation cannot be excluded.

Suspected Unexpected Serious Adverse Reaction (SUSAR) refers to a suspected and unexpected serious adverse reaction whose nature and severity exceed the information in the investigator's brochure, labeling, or product characteristic summary of the investigational drug.

Investigators will closely observe adverse events in subjects. All adverse events reported by subjects or observed by investigators from randomization to the end of the study or early withdrawal must be recorded in medical records or CRFs, including laboratory and auxiliary examinations, and at least include the name of the AE, time of occurrence, end time,

severity, whether corrective treatment was given, outcome, and causal relationship with the study.

During the study, changes in vital signs, physical examinations, clinical manifestations, and laboratory tests of subjects should be evaluated. When signing the informed consent form, the name and phone number of the researcher whom the subject can contact in case of emergency, or when reporting any medical symptoms or subject-related AEs, must be provided. Pre-existing toxic reactions or AEs in subjects before participating in the clinical study are only recorded as AEs if the grade increases by one or more levels compared with the baseline assessment results during the study.

CTCAE Grade	Equivalent	Definition
Grade 1	Mild	Mild physical discomfort, not affecting daily life and function
Grade 2	Moderate	Physical discomfort, affecting daily life and function, no indication for treatment

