12.2 Sample Size Calculation Process

88 cases
Sample size calculation process Based on preliminary experimental results, sample size was calculated using PASS, with a 20% dropout rate, resulting in a total sample size of 88 cases (22 cases in each group).

Input:

Power and Alpha

Power 0.95

Alpha 0.05

Group 4

Group Allocation Equal

Effect size

Means 30 34 50 53

K 1

σ 761519

Numeric Results
Means: 30 34 50 53

Power	Average	n	G	Total	K	Std Dev of Means	Standard Deviation	Effect Size	Alpha
0.9707	3.00	4		12	1.00	9.91	6.00	1.6515	0.0500
0.9875	4.00	4		16	1.00	9.91	7.00	1.4156	0.0500
0.9526	11.00	4		44	1.00	9.91	15.00	0.6606	0.0500
0.9526	17.00	4		68	1.00	9.91	19.00	0.5215	0.0500

One-Way Analysis of Variance F-Tests

Dropout-Inflated Sample Size (Continued)

Average Group Sample Size n	Group	Dropout Rate	Sample Size	Dropout-Inflated Enrollment Sample Size Ni	Expected Number of Dropouts Di
17.00	1 - 4	20%		17	22
	Total		68	88	5

13. Ethics of Clinical Research

The clinical study will follow the World Medical Association Declaration of Helsinki and other relevant regulations. Before the start of the study, the trial protocol will be implemented only after approval by the ethics committee. Before each subject is enrolled in the study, the investigator is responsible for fully and comprehensively introducing the purpose, procedures, and possible risks of the study to the subject or their agent, and a written informed consent form will be signed. Subjects should be informed that they have the right to withdraw from the study at any time. The informed consent form should be retained as a clinical study document for reference. The privacy and data confidentiality of subjects will be protected during the study.

14. Collection and Storage of Samples/Specimens

None.

15. Study Progress

Not available.

16. References

[2] Neira VM, Kovesi T, Guerra L, Campos M, Barrowman N, Splinter WM. The impact of pneumoperitoneum and Trendelenburg positioning on respiratory system mechanics during

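### Section 5.6 does not say that outcome collection to day 3 continues after a patient is terminated, so later pulmonary complications may go unrecorded

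*Protocol*

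**What the plan says.** Section 5.6 has two parts of different force.

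- The first is illustrative. It gives examples of situations in which continuing would be inappropriate, "including: worsening of the condition, serious adverse events, poor compliance, etc".
- The second is worded as a requirement: "Postoperative occurrence of surgery-related complications such as postoperative bleeding requiring reoperation should result in termination of the study".

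The rest of the Protocol bears on this as follows.

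- Section 4.4 lists a single endpoint: "Incidence of pulmonary complications within 3 days after surgery". The Protocol Summary and Sections 3.2 and 7 treat the same outcome as secondary. There the primary outcome is the time for dynamic compliance to return to baseline after recruitment.
- Sections 4.2, 6.3 and 6.5 place the group-specific oxygen concentration and the recruitment manoeuvres within surgery, with the last manoeuvre at its end.
- Section 9.1 counts "need for hospitalization or prolongation of hospitalization" among the criteria for a serious adverse event. It requires adverse events to be recorded from randomisation until the study ends or the patient withdraws early.
- Section 11 has recorded adverse events followed until they resolve or stabilise.
- Section 10 says the trial is to stop if a serious adverse event occurs during surgery.

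Nothing in the Protocol says that a terminated patient is still assessed to day 3.

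**The concern.** Stopping the study procedures and stopping the collection of outcomes are different decisions, and Section 5.6 does not separate them. Once surgery is over, no study intervention remains to be stopped, so ending a patient's participation can only remove follow-up.

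The required trigger, a postoperative surgical complication, can fall within the three days over which pulmonary complications are counted. Patients who are reoperated or deteriorating may plausibly have a higher pulmonary risk than the rest. Their absence would then be informative: it would lower the observed complication rates and, if termination differs between oxygen groups, distort the comparison. An analysis plan cannot repair this, because it cannot recover outcomes that nobody collected.

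**Working it through.** **1. The Protocol's own figure.** The sample size is for the primary outcome. Inputs from Section 12.2: "Means 30 34 50 53", "Group Allocation Equal", alpha 0.05, target power 0.95, 20% dropout. The final row uses SD 19.

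- SD of the four means = 9.91; effect size = 9.91/19 = 0.5215.
- With n = 17 per group: noncentrality = 4 × 17 × 0.5215² ≈ 18.5, df 3 and 64, power 0.9526. With n = 16, power is 0.9386.
- 17/(1 − 0.20) = 21.25, rounded up to 22 per group, 88 in total.

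The stated 88 reproduces. It was not set for pulmonary complications, and it allows for 5 of 22 lost per group.

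**2. Which events can be lost?**

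| Sequence | Is the event lost? |
|---|---|
| Reoperation on day 1, patient terminated, pulmonary complication on day 2 | Possibly. No day-3 assessment is required, and Section 9.1 stops recording new adverse events at early withdrawal. Section 11 follows up events already recorded. |
| Pulmonary complication occurs and itself prompts termination | It has already been observed. It is lost only if the patient is also removed from the analysis, which the text neither says nor rules out. |

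**3. Losing one event patient from an arm of 22.** The counts are assumed, since the Protocol gives none. The patient leaves both numerator and denominator.

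- 2/22 = 9.1% becomes 1/21 = 4.8%: 4.3 points lower.
- 4/22 = 18.2% becomes 3/21 = 14.3%: 3.9 points lower.
- 6/22 = 27.3% becomes 5/21 = 23.8%: 3.5 points lower.

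**4. A wider illustration.** Let p be the true rate, t the share terminated and RR their relative risk of a complication. Suppose the outcomes of all terminated patients are lost. The observed rate is q = p/(1 − t + t·RR), and the share of events lost is t·RR/(1 − t + t·RR). All three inputs are assumed.

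- p = 20%, t = 10%, RR = 3: q = 0.20/1.20 = 16.7%. Events lost = 0.30/1.20 = 25%, about 4.4 of 17.6 among 88 patients.
- Range: t = 5%, RR = 2 gives 0.10/1.05 = 9.5% lost; t = 20%, RR = 4 gives 0.80/1.60 = 50% lost.
- Two arms with the same true 20% but 5% versus 20% terminated, RR = 3: 0.20/1.10 = 18.2% against 0.20/1.40 = 14.3%, a spurious difference of 3.9 points. With RR = 2 it is 2.4 points and with RR = 4 it is 4.9.

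**5. Worst case within the planned dropout.** If all 5 allowed dropouts in an arm lack the outcome, the bounds on its rate are 5/22 = 22.7 points wide. For example, 3/17 observed (17.6%) is compatible with anything from 3/22 (13.6%) to 8/22 (36.4%).

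**The case against.** A reader might infer that Section 5.6 removes every patient who worsens or has a serious adverse event, and so removes patients because of the outcome itself. The text does not support that, for three reasons.

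- Worsening, serious adverse events and poor compliance are offered as examples; only the reoperation sentence is worded as a requirement.
- A pulmonary complication that triggers termination has by then been seen, and the outcome is a simple yes or no. Sections 9.1 and 11 have it recorded and followed.
- Section 5.6 does not say that terminated patients leave the analysis. Where the Protocol means exclusion, as for Group A in Section 5.4, it says so.

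The heading of Section 5.6 speaks of terminating the study, and Section 10 speaks of stopping the trial, so a trial-level reading is possible. Poor compliance and a single reoperation fit an individual patient better. On the trial-level reading, one reoperation would end the trial. Either way the wording needs clarifying.

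The practical effect may also be small. Patients are elective, ASA I–II, aged 18–64, with blood loss of at most 500 ml, so frequent termination that depends on the oxygen group is not shown. A shift of 3.5 to 4.3 points is well below the standard error of a two-arm difference at 4/22, √(2 × 0.182 × 0.818/22) ≈ 12 points.

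All of this stands and limits the point. It does not answer the case of a complication arising after a reoperation, for which no assessment is required.

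**Conclusion.** The point holds in a limited form. Section 5.6 requires termination for a postoperative event that can fall inside the 3-day window, and nothing in the Protocol keeps outcome assessment going afterwards. On the per-patient reading, which fits the examples best, pulmonary complications after a reoperation or other terminating event may go unrecorded. Complications that themselves cause termination are at risk only if terminated patients are also left out of the analysis, and that is open.

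The damage is confined to postoperative outcomes, chiefly 3-day pulmonary complications; postoperative termination leaves the intraoperative primary outcome intact. The size and direction of any bias between groups are unknown. The 3.5 to 4.3 points per lost event patient rest on assumed counts of 2 to 6 in 22. The loss of 9.5% to 50% of events rests on assumed termination of 5–20% and relative risks of 2–4, with every terminated patient's outcome lost. These figures illustrate the mechanism and do not estimate it. The change is worth making because it costs little.

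**What to change.** Add to Section 5.6:

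- Termination applies to the individual patient's study procedures and not to outcome collection.
- PACU hypoxemia and 3-day pulmonary complications are collected and counted in the assigned arm for all randomised patients, including after a serious adverse event or reoperation, unless the patient withdraws consent to data collection.

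Reconcile the wording of Section 5.6 with the trial-level wording in Section 10, so that it is clear which provision concerns a patient and which the trial. The clinical criteria for stopping are left as they are, and the sample size does not change. Any sensitivity analysis for reoperated patients can be left to the statistical analysis plan.

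The cost is a sentence or two and minor follow-up effort over three days. One drawback is that some counted complications may be due to the reoperation rather than the oxygen concentration.

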6.1 Study Grouping

Grouping: Group A: FiO₂=30% (if SpO₂<94%, increase FiO₂; if FiO₂≥40%, the patient was excluded); Group B: FiO₂=40%; Group C: FiO₂=60%; Group D: FiO₂=80%. Inspired oxygen concentrations were adjusted to the respective group levels after the start of surgery.

6.2 Intervention Measures

Lung recruitment

6.3 Study Intervention Protocol

Patients entered the operating room, preoxygenated for 3 minutes, followed by anesthesia induction. After the drugs took full effect, tracheal intubation was performed. Inspired oxygen concentrations were adjusted to the respective group levels after the start of surgery. The first lung recruitment was performed 10 minutes later. The second lung recruitment was performed after lung compliance returned to baseline. Respiratory mechanics parameters, hemodynamic parameters, etc., were recorded. The incidence of hypoxemia during PACU stay and postoperative atelectasis evaluated by ultrasound were recorded.

6.4 Concomitant Medications

There were no concomitant medications in this study.

6.5 Study Flowchart

![img](Patients enter the operating room

Preoxygenation followed by tracheal intubation

Adjust to group-specific FiO₂ after surgery starts

Group A: FiO₂ 30%

Group B: FiO₂ 40%

Group C: FiO₂ 60%

Group D: FiO₂ 80%

First lung recruitment after 10 minutes

Record the duration of improved lung compliance

Next lung recruitment after compliance returns to baseline, and so on

All patients undergo lung recruitment immediately at the end of surgery,

Transfer to PACU, record incidence of hypoxemia and duration of oxygen therapy)

6.6 Study-Related Laboratory Tests

Liver and kidney function, blood routine, coagulation function, blood gas analysis

6.7 Study-Related Imaging Examinations

Electrocardiogram

7. Efficacy Evaluation Criteria

Observation of primary outcome indicators: Time for dynamic lung compliance (Cdyn) to return to baseline after lung recruitment. Respiratory mechanics parameters and hemodynamic parameters at T1-T5 were recorded, including Cdyn, PIP, Ppeak, Pplat, Vt, PEEP, MP, Pdrive, BP, HR;

Observation of secondary outcome indicators: Degree of atelectasis immediately after extubation, evaluated by lung ultrasound; oxygenation index at T0-T5; incidence of hypoxemia and duration of oxygen therapy during PACU stay; pulmonary complications within 3 days after surgery, evaluated by postoperative chest X-ray or CT, with atelectasis assessed by lung ultrasound.

8. Observation Items and Detection Time Points

Before the first lung recruitment (RM1) after surgery starts (T1), immediately after RM1 (T2), before RM2 (T3), immediately after RM2 (T4), and immediately at the end of surgery (T5). Primary and secondary outcome indicators were observed. Degree of atelectasis immediately after extubation, evaluated by lung ultrasound; oxygenation index at T0-T5; incidence of hypoxemia and duration of oxygen therapy during PACU stay; pulmonary complications within 3 days after surgery, evaluated by postoperative chest X-ray or CT, with atelectasis assessed by lung ultrasound.

9. Observation of Adverse Events

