12.1 Statistical Methods

All data were statistically analyzed using SPSS 26.0 software, with $P<0.05$ indicating a statistically significant difference. Count data were expressed as cases or percentages and analyzed using the Chi-square test or Fisher's exact test. Normality of measurement data was evaluated using the Kolmogorov-Smirnov test or Shapiro-Wilk test. Measurement data conforming to a normal distribution were expressed as mean \pm standard deviation ($x\pm s$) and analyzed using the t-test; count data with repeated measurements were analyzed using one-way ANOVA; skewed or unknown-distribution measurement data were expressed as median (interquartile range) [median (IQR)] and analyzed using the Mann-Whitney U test.

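### The primary endpoint, time for Cdyn to return to baseline, is cut off when surgery ends first, and the named tests do not handle cut-off times; the effect is small at planned operation lengths

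*Protocol*

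**What the plan says.** Section 7 defines the primary endpoint: "Observation of primary outcome indicators: Time for dynamic lung compliance (Cdyn) to return to baseline after lung recruitment". The flowchart in section 6.5 gives the matching instruction, "Record the duration of improved lung compliance".

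The timing comes from sections 4.2 and 8. FiO2 is set once surgery has started, and then "The first lung recruitment was performed 10 minutes later" (RM1). RM2 follows only when compliance is back at baseline. Section 4.2 adds "All patients underwent lung recruitment immediately at the end of surgery". Section 8 places T1 before RM1 and T2 straight after it, and continues "before RM2 (T3), immediately after RM2 (T4), and immediately at the end of surgery (T5"). Eligibility (section 5.2) requires "Expected operation time ≥1.5 hours", which is an expected and not an achieved duration.

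For the analysis, section 12.1 opens by covering all data. Normally distributed measurements are "analyzed using the t-test"; skewed ones, or those of unknown distribution, are "analyzed using the Mann-Whitney U test". The summary repeats both tests in a list that ends in etc. Section 12.2 sizes the trial with a one-way ANOVA F-test. No section says what value is given to a patient whose Cdyn has not returned when surgery ends.

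**The concern.** The endpoint is a time to an event, and the design can stop the clock before the event. The recruitment at the end of surgery goes ahead whether or not Cdyn has returned. A slow patient then never reaches RM2 and has no T3, and the only thing known is that the time exceeds the observed window.

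If such a patient is left out, the longest times are removed. If the cut-off is entered as though Cdyn had returned, those times are understated. Under the planning values this happens almost only in the two arms with long return times, so both handlings pull the differences between arms toward zero. The amount depends on how long operations last and not on FiO2. A choice between the two handlings made after the data are seen would also move the result.

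**Working it through.** **Inputs.** Means 30, 34, 50, 53 (section 12.2); SDs 7, 6, 15, 19 (summary, sample size row); alpha 0.05; 17 per arm analysed and 22 enrolled; RM1 at 10 minutes; planned operation at least 90 minutes.

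**Assumptions.** The unit is minutes. Times are normal. SDs pair with means in listed order. The planning values are not themselves cut off. The clock runs from RM1 to first return (T1 to T3), which section 7 does not state. The protocol does not say which FiO2 group has which mean, so the arms are named here by their means.

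**The plan's own figure.** The grand mean is 41.75. The sum of squared deviations is 138.06 + 60.06 + 68.06 + 126.56 = 392.75, so the SD of the means is √(392.75/4) = 9.91, as printed. With n = 17 and SD 19, λ = 17 × 392.75/361 = 18.5, and the noncentral F gives power 0.9526, as printed. 17/0.8 = 21.25, so 22 per arm and 88 in total. The stated sample size reproduces.

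**Share cut off and effect on the means.** Let W be the window after RM1 and z = (W − mean)/SD.
- Unfinished share = 1 − Φ(z)
- Mean if unfinished patients are dropped = mean − SD × φ(z)/Φ(z)
- Mean if the cut-off is entered = Φ(z) × dropped mean + (1 − Φ(z)) × W

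Example, 53 arm, W = 80: z = 27/19 = 1.42, so 7.77% are unfinished. The dropped mean is about 50.0 and the entered mean about 52.3. The 30 arm is untouched, so the contrast is 20.0 or 22.3 in place of 23. In the 50 arm z = 30/15 = 2, so 2.28% are unfinished. Expected number: 22 × (0.0228 + 0.0777) = 2.2 of 88.

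| Window (operation) | Unfinished, 50 / 53 arm | Of 88 | Contrast, dropped | Contrast, entered |
|---|---|---|---|---|
| 70 min (80 min) | 9.1% / 18.5% | 6.1 | 16.8 | 21.1 |
| 80 min (90 min) | 2.3% / 7.8% | 2.2 | 20.0 | 22.3 |
| 90 min (100 min) | 0.4% / 2.6% | 0.6 | 21.8 | 22.8 |
| 100 min (110 min) | 0.04% / 0.7% | 0.2 | 22.6 | 23.0 |

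The 30 and 34 arms round to 0% throughout. The 70-minute row is illustrative: it supposes that surgery ends 10 minutes short of the planned minimum.

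**Distribution check.** Lognormal times with the same means and SDs give 4.0% and 8.7% unfinished at W = 80 (contrast 19.0 dropped, 21.7 entered), and 0.6% and 2.3% at W = 100 (21.6, 22.7).

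**Mixed windows (simulated, normal times).**

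| Windows | Dropped | Entered | Kaplan-Meier restricted mean to 80 min |
|---|---|---|---|
| Uniform 80–140 | 22.5 | 22.9 | 22.3 |
| Uniform 60–100 | 19.5 | 21.8 | 22.4 |

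The first two columns move with operation length; the restricted mean hardly does.

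**Power (simulated, common SD 19, W = 80).** At 17 per arm the F-test has 0.954 with complete data, 0.911 with unfinished patients dropped and 0.954 with the cut-off entered. At 22 per arm the figures are 0.989, 0.970 and 0.988. With the group-specific SDs and 17 per arm, every method gives 0.998 or more.

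**The case against.** **A rank test can cope.** Mann-Whitney needs only the order of the values. If all windows were equal, unfinished patients could tie at the highest rank, which is correct information. The median and quartiles would not move either: the highest upper quartile under the planning values is 53 + 0.674 × 19 = 65.8, below even a 70-minute window. A four-group rank test, which the protocol does not name, has simulated power of about 0.935 at 17 per arm with SD 19 and W = 80. This stands, so it would be wrong to infer that the named tests force dropping or capping. But windows will differ with operation length. A patient cut off at 80 minutes cannot then be ranked against one who returned at 95, and the protocol states no ranking rule.

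**It is immaterial.** Even if every operation took the minimum 90 minutes, capping costs 0.7 of 23 and no power. The larger loss comes from dropping patients, which the protocol nowhere prescribes. This stands as a limit on size. The protocol does not bar dropping, however, and a patient without a return time would naturally go missing from the named tests.

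**Shorter operations are hypothetical.** That is correct. Eligibility rests on expected time, so they can occur, but nothing in the protocol supports any particular share.

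**It belongs in the SAP.** A SAP could add a censoring rule. The protocol has nevertheless already named tests for all data, and it lists neither return status nor end-of-observation time among the items to record. T5 does not settle status, because section 8 does not say whether it precedes the final recruitment.

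**Conclusion.** The point holds as a modest improvement. The primary endpoint can be cut off by the end of surgery, and the tests the protocol names do not handle that when operation lengths differ. At the shortest planned length about 2 of 88 patients are affected, and the largest contrast falls from 23 to about 20.0 (dropped) or 22.3 (entered). With a 100-minute window the effect is near zero under normal times, and slightly larger if times are skewed. These sizes rest on the unit, distribution, SD pairing and RM1 starting point assumed above.

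Three stronger conclusions are tempting but unsupported:
- **The trial is too small.** Its sample size reproduces. Dropping the unfinished from 22 per arm still leaves power of about 0.97 under the conservative SD.
- **The result will be badly diluted.** That needs many operations to end early, and the protocol gives no such share.
- **Log-rank must become the primary test, with more patients.** Its power is about 0.92–0.93 at 17 per arm with a common SD of 19, below the F-test's 0.95, so that change is a debatable trade and not a correction. Under the group-specific SDs used for the bias figures, the power question does not arise.

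**What to change.** **Section 7.** Define the endpoint as the time from RM1 to the first return of Cdyn to its baseline, say what that baseline is, and censor at the end of surgery before the final recruitment. Record whether Cdyn returned (yes/no) and the time at which observation ended.

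**Section 12.1.** State that unfinished patients are not excluded and are kept as censored. Compare the groups on a Kaplan-Meier-based restricted mean time to a horizon stated in advance (for example 80 minutes). Give Kaplan-Meier curves and a four-group log-rank test as supportive analyses.

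**Cost.** Two recorded items and some wording. The contrast is reported as a restricted mean, about 22.3 under the planning values, so it does not recover the full 23; the gain is a target that does not shift with operation length. The method assumes that the end of surgery is unrelated to when Cdyn would have returned. With a common 80-minute window the restricted mean equals the entered-cut-off contrast, which has power of about 0.95 at 17 per arm, so the sample size can stay as it is.
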